#### 9.4.7 Baseline Descriptive Statistics

Summary statistics of baseline variables (e.g., demographics, time from stroke onset, aphasia type, WAB-R AQ, all baseline assessments) will be compared by treatment groups. Dichotomous variables will be summarized as number (%). Percentages will be calculated based on the number of participants with available data for that variable. Continuous variables will be summarized by the mean and standard deviation (SD). Ordinal data will be presented as median (IQR).

## 9.4.8 Sub-Group Analyses

Gender, Race, Ethnicity: All eligible subjects of both sexes and all races and ethnic groups will be approached to participate in the trial. Recruitment and retention of women and minorities will be monitored throughout the trial. Although we do not anticipate differential treatment effects based on sex, race, or ethnicity, our analyses will explore clinically important differences in these subgroups. Randomization should ensure that the allocation to treatment groups is unbiased and balanced between males and females and different racial and ethnic groups. At the end of the trial, the primary analysis will be repeated within sex subgroups and within race/ethnicity groups. If differences in the magnitude of the treatment effect are observed within a sex, race, or ethnicity subgroup, they will be reported to the scientific community.

#### 9.4.9 Tabulation of Individual Participant Data

Individual participant data will not be listed by measure and time point in the final analysis; however, individual participant listings may be included in Data and Safety Monitoring Board (DSMB) reports for purposes of monitoring trial quality.

#### 9.4.10 Exploratory Analyses

# **Exploratory Endpoints:**

Communicative Effectiveness Index (CETI) Apraxia of Speech Rating Scale (ASRS 3.0) WAB-R

For the exploratory endpoints, the mean change from baseline to 1 week and 3 months post of each SET group will be compared to control with 95% confidence intervals.

#### 9.4.11 Scoring of speech samples and evaluation of potential confounders

As described above, all baseline and treatment videorecorded discourse samples will be scored centrally at the Aphasia Lab at UofSC using AphasiaBank, with the exception of transcription and scoring of the ASRS 3.0, which will be completed by an expert scorer at UoU. Special care will be taken to evaluate the influence of potential confounders, such as AOS (rated

on the ASRS), speech repetition scores (WAB-R, PRT), single word (WAB-R), and sentence level comprehension. These will be input into the multiple linear regression analyses used to define determinants of the primary outcome as a sensitivity analysis. Since SET has not been systematically studied as a potential clinical treatment, the goal of this project is to determine if SET is associated with a robust effect size regardless of the underlying source of impairment, but it is very likely that cognitive and linguistic factors that vary across persons with non-fluent aphasia may influence SET outcome to different degrees. We will assess these variations and the overall benefit of SET by systematically assessing the effect size of SET and examining individual characteristics that relate to treatment response.

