# Western Aphasia Battery-Revised (WAB-R)

The WAB-R will characterize the participant's overall language impairment through the evaluation of the main clinical aspects of language functioning, including speech content, speech fluency, auditory comprehension, repetition, naming, and reading. It allows for the differentiation of these specific language abilities, as well as the classification of aphasia type (see Table 6 below). The WAB-R also yields a composite score, the Aphasia Quotient (AQ), which provides an overall measure of severity, in which lower scores denote more severe aphasia (see Table 7 below). For diagnostic purposes, non-fluent aphasia is defined by WAB-R Auditory Comprehension score >4 and WAB-R Fluency score <6, falling under the categories of global, Broca's, transcortical motor, or transcortical mixed aphasia.

Table 6. Aphasia Classification Criteria

Aphasia Type	Fluency*	Auditory Verbal Comprehension	Repetition	Naming and Word Finding
Global	<5	0-3.9	0.49	<7
Broca's	<5	4-10	0-7.9	<9
Isolation	<5	0-3.9	5-10	<7
Transcortical	<5	4-10	8-10	<9
Motor				
Wernicke's	>4	0-6.9	0-7.9	<10
Transcortical	>4	0-6.9	8-10	<10
Sensory				
Conduction	>4	7-10	0-6.9	<10
Anomic	>4	7-10	7-10	<10

\*In this study we will use a Fluency score of <6 for inclusion of participants with mild or improving non-fluent aphasia as defined by the description of Fluency score 5 in the WAB-R administration and scoring manual.

Table 7. Aphasia Quotient (AQ) and Severity

AQ	Severity
0 < AQ ≤ 25	Very severe
25 < AQ ≤ 50	Severe
50 < AQ ≤ 75	Moderate
75 < AQ ≤ 93.7	Mild
93.7 < AQ ≤ 100	No aphasia

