# 8.0 Study Assessments and Procedures

#### 8.1 Efficacy Assessments

#### 8.1.1 Baseline measures

The WAB-R will be obtained at participant screening to determine if the participant fits criteria for non-fluent aphasia (WAB-R Comprehension score > 4 and WAB-R Fluency score < 6). See Table 6 for aphasia classification chart. If the participant does not classify as having non-fluent aphasia, this is considered a screen failure. The participant will undergo an MRI to determine stroke eligibility criteria, unless MRI images from the stroke are made available to the study team for review. The ASRS 3.0, PPTT, and WAIS-III will be obtained for the purpose of linguistic assessments and participant description in publications. The ASRS 3.0 measures the presence and severity of AOS; the PPTT assesses amodal semantic processing of nouns; and the WAIS-III measures non-verbal abstract problem solving and inductive and spatial reasoning. The SAQOL-39g will be given to assess quality of life for each individual with aphasia. All baseline language assessments will be videorecorded for offline scoring. Recording will include the participant from head to torso, and all recordings will be stored on Box.

Speech repetition and comprehension: We will employ detailed measures of speech repetition and comprehension to refine the identification of subtypes of aphasia and improve the evaluation of the influence of these variables on the effectiveness of SET. As part of the WAB-R, participants will complete the repetition subtest involving single words, phrases, as well as shorter and longer sentences. In addition, all participants will be administered the PRT, involving real words. For detailed assessment of auditory comprehension, we will rely on subtests from the WAB-R.

The mechanisms of action of SET will be determined from the comprehensive behavioral assessment as described in Table 1 above. More specifically, we will define whether fluency improvements with SET are supported by repetition, speech comprehension, or residual fluency, based on the multi-faceted speech and cognitive evaluations.

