## 7. ANALYSIS OF THE PRIMARY ENDPOINT

The primary outcome is VPM which is a continuous value greater than 0. It is collected at baseline and after 3 months post treatment. The primary analysis will calculate the change in average VPM (from the Narrative Story Telling Task and Procedural Story Telling Task) from baseline. The statistical model will be a repeated measures model (SAS® MIXED procedure with REPEATED subcommand). The model will include the following fixed effects: categorical visit (1 week, 3, and 6 months post treatment period) by treatment group (class variable) interaction, site, baseline aphasia severity score (centrally scored), baseline VPM and age. The estimated difference (95% confidence intervals) in change between each SET duration group and control group will be reported. The standardized mean difference for each SET duration versus control will be used to select the best dose of SET. Since this study is not powered for direct comparison with control, no p-values will be reported.

Empirical robust sandwich estimators will be used to account for the randomization procedure in order to appropriately estimate the marginal treatment effect. The unstructured covariance matrix for repeated observations within subjects will be used. In case the model will not converge, the maximum-likelihood (ML) estimation method will be used instead of the default restricted ML (REML). If the model still does not converge, a simpler covariance structures with less parameters will be used, according to the following order: heterogeneous autoregressive(1) (ARH(1)), heterogeneous compound symmetry (CSH), autoregressive(1) (AR(1)), and compound symmetry (CS). The estimated means at the 3 month post visit of the change from baseline in VPM will be compared for the SET 3 week group versus control, SET 4.5 week versus control, SET 6 week versus control, and the combined SET durations versus control. The SAS code for this analysis is as follows:

```
PROC MIXED EMPIRICAL;
  CLASS SUBJID ARM VISIT CENTER;
  MODEL CHANGE=ARM|VISIT CENTER BASE_WABAQ BASE_VPM AGE;
  REPEATED VISITNUM / TYPE=UN SUBJECT=SUBJID R RCORR;
  LSMEANS ARM*VISIT/ cl;
RUN;
```

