## **16. EVALUATION OF POTENTIAL CONFOUNDERS**

As described above, all baseline and treatment video-taped discourse samples will be scored centrally at the Aphasia Lab at USC using AphasiaBank. Special care will be taken to evaluate the influence of potential confounders such as apraxia of speech (rated on the ASRS), speech repetition scores (WAB-R, PRT), single word (WAB-R) and sentence level comprehension. As a sensitivity analysis, the primary analysis will be repeated while adjusting for these potential confounders to define determinants of the primary outcome. Since SET has not been systematically studied as a potential clinical treatment, the goal of this project is to determine if SET is associated with a robust effect size regardless of the underlying source of impairment, but it is very likely that cognitive and linguistic factors that vary across persons with non-fluent aphasia may influence SET outcome to different degrees. We will assess these variations and the overall benefit of SET by systematically assessing the effect size of SET and examining individual characteristics that relate to treatment response. This will be accomplished by assessing for interaction effects of potential confounders and treatment group.

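### The model meant to identify determinants of VPM adjusts for WAB-R AQ alongside its own repetition and comprehension parts, so those main-effect coefficients can mislead

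*Protocol*

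**What the plan says.** - **Protocol 9.4.11** names apraxia of speech (ASRS) and "speech repetition scores (WAB-R, PRT), single word (WAB-R), and sentence level comprehension" as possible confounders, and continues: "These will be input into the multiple linear regression analyses used to define determinants of the primary outcome as a sensitivity analysis". This sentence does not mention AQ.
- **SAP 16** gives almost the same list, including "speech repetition scores (WAB-R, PRT), single word (WAB-R) and sentence level comprehension", and fixes the model: "As a sensitivity analysis, the primary analysis will be repeated while adjusting for these potential confounders to define determinants of the primary outcome". The primary covariates therefore stay in.
- **SAP 7** gives the primary model as "MODEL CHANGE=ARM|VISIT CENTER BASE_WABAQ BASE_VPM AGE", so baseline AQ is one of those covariates.
- **Protocol 1.4** describes AQ: "The WAB-R also yields a composite score, the Aphasia Quotient (AQ), which provides an overall measure of severity". It lists comprehension and repetition among the domains of the battery, but gives no formula or weights for AQ.
- **Protocol 8.1.1** says where the comprehension scores come from: "For detailed assessment of auditory comprehension, we will rely on subtests from the WAB-R".
- For differences in response to SET, SAP 16 plans separate interactions between these scores and treatment group. It does not say whether AQ-by-arm is among them.

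Neither document removes AQ from this model, replaces it with a non-overlapping part, or says how a coefficient is to be read with AQ held fixed.

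**The concern.** A composite stands in the model beside its own parts. At a given AQ, a participant with a higher repetition score must score lower elsewhere in AQ. The repetition coefficient is then a contrast between repetition and the remaining parts, while a reader will take it as the effect of repetition. The same holds for comprehension.

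Protocol 2.2.6 leaves open whether success with SET depends on repetition or comprehension impairment, and Protocol 2.2.4 treats individual determinants of success as central to the follow-on trial. A table of coefficients that shows repetition as irrelevant or harmful, when that comes from the choice of covariates, could be carried into the design of that trial. More participants would not cure it, because the quantity estimated is not the one intended.

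**Working it through.** **No figure to reproduce.** The documents give no sample size, power or expected coefficient for this analysis.

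**Inputs from the documents.** n=80, 20 per arm (Protocol 4.1). SD of VPM change 1.98 in the pilot (Protocol 4.3.1), rounded to 2 in Protocol 9.2.2.

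**Assumptions, not in the documents.** The AQ weights, the subscore SDs and correlations, and the size of each determinant's effect.

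**Step 1: algebra.** Let the outcome be Σ βj·Sj over the subscores and AQ = Σ wj·Sj. Enter AQ, repetition (R) and comprehension (C). If the AQ parts not entered share one ratio β/w = k, their contribution is k·(AQ − wR·R − wC·C). The coefficient of R is therefore

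βR − k·wR.

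- All parts equally important, w=2, β=0.2, so k=0.1: 0.2 − 0.1×2 = 0.
- Only the unentered parts matter: 0 − 0.1×2 = −0.2.
- Only entered scores matter, k=0: βR, which is correct.

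**Step 2: simulation with four subscores.** SD 1, correlation 0.5, AQ an equal-weight sum, residual SD 1.9, 4,000 trials, least squares at one visit. Covariates were arm, site, baseline VPM, age, ASRS, comprehension and repetition; PRT was left out. Spontaneous speech and naming are each worth 0.6 VPM per SD.

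| True repetition effect | With AQ | With non-overlapping part |
|---|---|---|
| 0 | mean −0.61; interval below 0 in 32% | mean 0.00 |
| 0.6 | mean 0.01; interval above 0 in 3% | mean 0.61; interval above 0 in 53% |

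The SE is 0.41 with AQ and 0.29 without. The rates follow from these by normal approximation: −0.61/0.41 = −1.49 and P(Z < −1.96 + 1.49) = 0.32; 0.61/0.29 = 2.10 and P(Z > 1.96 − 2.10) = 0.56, close to the simulated 53%.

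Variations on the null case:
- Correlation 0.7 to 0.3: 20% to 40% falsely negative.
- Spontaneous speech double-weighted: mean −0.36, 17%. Here k is 0.3 for speech and 0.6 for naming, so the formula puts the coefficient between −0.3 and −0.6.
- Effects of 0.3 instead of 0.6: mean −0.30, 12%.
- Residual SD 2, the rounded figure of Protocol 9.2.2: mean −0.61, 31%.

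**Step 3: second simulation with five subscores.** AQ = 2×(content + fluency + comprehension + repetition + naming), 0.2 VPM per point for each real determinant, SDs 1.3-2.5, correlations 0.2-0.7, residual SD 2, 1,500 trials.

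| Case | With AQ | With non-overlapping part |
|---|---|---|
| All five matter equally | 0.00; detected in 1.5-2.5% | +0.20; detected in 25-51% |
| Repetition and comprehension irrelevant | −0.20; falsely negative in 16-33% | 0.00; about 3% |
| Repetition alone matters | +0.20; detected in 15-34% | +0.20; detected in 26-52% |

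The variance inflation factor for repetition falls from 1.9-5.1 to 1.1-2.7. When a noisy single-word score replaces the full comprehension score, the null case still gives −0.17 to −0.18 (13-28%). Adding a PRT-like score as well gives 11-16%, mainly because the SE rises (0.147 to 0.196 at correlation 0.4).

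**Step 4: what does not move.** If the whole repetition and comprehension subscores are entered, replacing AQ by the sum of its remaining parts re-expresses the same model. The repetition coefficient becomes the old one plus 2 times the AQ coefficient. At correlation 0.4, −0.006 + 2×0.102 = 0.198 (fitted 0.199), and −0.195 + 2×0.099 = 0.003 (fitted 0.004). The treatment estimate is the same either way (0.983 and 0.983, 1.022 and 1.022; true value 1.0).

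**Step 5: interactions.** With AQ as a main effect only, the repetition-by-SET estimate lay between 0.07 and 0.38 in the cases tried. It never fell to zero or below, and it is the same whether AQ or its remainder is the main effect. With AQ-by-arm added, the artefact returns: about 0 when all parts modify response equally, and about −0.20 when only the unentered parts do.

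**The case against.** The strongest case against is that this is a labelled sensitivity analysis whose other stated aim is to see whether the SET effect holds up whatever the source of impairment. That aim is met, because the treatment contrasts do not change. A coefficient at fixed overall severity is also a legitimate conditional quantity. Who benefits from SET is a question of moderation, and SAP 16 answers it through interactions, not through main effects pooled over SET and control.

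Most of this stands, and it limits the point. A reader might infer that the analysis gives reversed answers about who responds to SET, or that the choice of duration is at risk. The documents support neither. Response is assigned to the interaction terms, AQ is not named among the scores to be interacted, and the selection rule (SAP 9) uses the primary model.

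Three further limits also stand. The Protocol sentence does not itself put AQ in the model; that follows from SAP 16 read with SAP 7. The sizes depend on undocumented weights and effects. If the speech effect acts partly through baseline VPM, which is already a covariate, the null repetition coefficient shrinks to −0.31 to −0.46, with 12-18% falsely negative.

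What does not stand is that the label disposes of the matter. SAP 16 gives identifying determinants as a purpose of the refit, and nothing tells the reader that the coefficients are contrasts within AQ.

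**Conclusion.** The point holds for the main-effect coefficients of the WAB-R repetition and comprehension scores in the SAP 16 model, and only there. Its direction needs two things: AQ is a positively weighted sum that includes these scores, and AQ parts not entered separately also raise the outcome. Given both, the coefficients are pulled downward. With equal weights and equal effects, a real determinant averages zero.

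At n=80, under the assumptions shown, an irrelevant repetition score is falsely negative in roughly 12-40% of trials. A real and equal effect is found in about 2-3%, against about 50% in the first simulation and 25-51% in the second once AQ is replaced, and less often if PRT is entered as well. If only the entered scores matter, the estimates are unbiased but less precise.

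All rates come from single-visit least squares instead of the full repeated-measures model, so they indicate scale only. Entering both WAB-R repetition and PRT costs precision and is not an error in itself.

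**What to change.** In SAP 16 and Protocol 9.4.11, for the determinant coefficients only:

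1. Replace BASE_WABAQ with the AQ component subscores not otherwise in the model. Take the components from the WAB-R scoring manual the Protocol already cites, since the documents do not give the formula. If only some comprehension subtests are entered, the rest of the comprehension score belongs with the replacement.
2. State that AQ-by-arm will not be entered together with subscore-by-arm terms.
3. Preferably enter one repetition measure at a time (WAB-R repetition or PRT).

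Keep AQ in the primary model. Still report the treatment contrasts from the sensitivity model, because they are the robustness check that both documents ask for.

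The cost is a sentence or two and a changed covariate list. The subscores come from the WAB-R already administered and centrally scored at baseline, so no new data are needed. Entering the remaining parts separately instead of as a sum uses a few more degrees of freedom.

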# 10.0 Regulatory, Ethical, and Study Operational Considerations

# 10.1 Informed Consent Process

The consent documentation contains all required regulatory elements and has been approved by the central IRB. The consent also contains HIPAA authorization to use and disclose (release) medical information.

#### 10.2 Consent Procedures and Documentation

Informed consent can be obtained in written fashion by one of the members of the study team. Participants will be provided with ample time to review the consent document prior to discussion with a member of the study team. The nature of the study will be explained by a member of the study team in lay terms. If the potential participant agrees to participate in the study, they will sign and date the informed consent and HIPAA forms (or combined consent/HIPAA if applicable). They will also be informed that they may choose to withdraw from the study at any time. Participants will be informed that their decision regarding participation will not affect their clinical care in any way. A copy of the signed informed consent and HIPAA will be provided to participants.

Alternatively, electronic consent (eConsent) will be obtained through the REDCap system. A member of the research team will reach out to the participant by phone to provide details of the study. If the participant agrees to participate, a link to the REDCap eConsent will be provided to the participant via a hyperlink (text or email), and a member of the study team will review the consent document over the phone or via videoconferencing with the participant. The participant will electronically sign the eConsent and submit the REDCap survey. The study team member will then electronically sign the eConsent and print a PDF of the document. The signed PDF willl be emailed or mailed to participants for their records. eConsent will be implemented at sites that support this method of consent.

#### 10.3 Study Discontinuation and Closure

If the study is prematurely terminated or temporarily suspended, the PI will promptly inform study participants, the IRB, and sponsor and provide the reason(s) for the termination or temporary suspension. When a study is prematurely terminated, refer to Section 7, Study Intervention Discontinuation and Participant Discontinuation/Withdrawal, for handling of enrolled study participants.

## 10.4 Confidentiality and Privacy

Each participant will be given an identification number through the WebDCUTM and all baseline and outcome measure data will be linked to this number without any identifying information of the participant. Each participant will have a binder that will contain demographic and baseline characteristics (refer to Table 3). The person obtaining this information will have gone through CITI research ethics training and been approved by the IRB. All binders with identifying information will be stored in a locked location at the site. Assessments will be performed via telehealth and videos of participants that have been recorded will be stored on Box, MUSC's approved cloud storage device. Only those who are IRB approved will have access to these videos. A central technology support specialist will have access to participant PHI across sites in order to monitor audio/visual quality of videos and assist with technology with participants in real-time

#### 10.5 Future Use of Stored Data

Data stored on Box and WebDCUTM will be used for data analyses while the study is actively enrolling and after enrollment has ended. All data stored on WebDCUTM will be deidentified with each participant having their own unique identifier. Audio-video recordings of participants will be stored on Box, and only those who are IRB approved will have access to these recordings.

